## 6. STUDY PROCEDURES

Visits include screening, baseline, and follow-up for months 1, 3, 6, 9, and 12 for those enrolled prior to May 2022, and months 1, 3 and 6 for those enrolled after May 2022. Procedures outlined in Appendix 2. A cross-sectional survey will be sent out to all participants to collect information on behavior and PrEP changes due to COVID-19 pandemic and distancing regulations.

### 6.1 Visit Procedures

#### 6.1.1 Scheduling

Once recruited respondents have completed the online screening, study site staff will contact the eligible participants, and schedule a baseline visit for either at the local study site or via Zoom. Participants will be seen at the research clinical space at their local study site or via Zoom telehealth consultation.

After baseline procedures are completed (Section 6.2) and participants are randomized, study staff will schedule telemedicine appointments with intervention arm participants via electronic

messages. Control arm participants will receive an active linkage to care scheduled visit to study identified standard of care clinics, or to the participant's preferred local provider, for the PrEP 1 month follow-up visit.

#### **6.1.2 Visit Reminders**

Electronic reminder mechanisms for intervention participants will be sent, including app notifications and/or electronic messages. Staff will use electronic messages, telephone calls, or emails to serve as reminders for scheduled consultation visits.

### **6.2 Baseline Visit**

All baseline procedures are identical for both intervention and control participants and occur after participant provides consent. Participants will be directed to download the study app, P@H, and will be able to take the baseline survey through the app. Participants will be called and scheduled for a baseline visit and instructed to have materials necessary for enrollment in PrEP financial assistance programs. Study consent will be reviewed with participants at the clinic visit and eligibility will be confirmed for stage 1 and assessed for stage 2 (section 3.5.2). Participants will talk with a healthcare provider about initiating PrEP and any concerns they have regarding PrEP. The baseline survey will assess domains including demographics, healthcare, HIV/STI knowledge and testing history, PrEP knowledge and interest, sexual history including overall and detailed partner-level data, substance use history including injection drug use, and scientifically validated scales for depression, anxiety, resilience, self-efficacy, experience of racism, and stigma.

Participants will conduct self-finger prick rapid HIV test either at the clinic or from home test kit. If negative, they will proceed to have specimens collected to be tested for creatinine, HIV AbAg (4th gen), Hepatitis B (HBsAg), Hepatitis C antibody (anti-HCV), syphilis (EIA with reflexive RPR), and oral, pharyngeal, and rectal gonorrhea/chlamydia (NAAT). Laboratory testing will be conducted by CLIA-certified laboratories at each site's locally contracted laboratory. If a participant has completed these labs as part of PrEP initiation at the clinic in the past 3 months, only the HIV AbAg (4th gen) test will need to be repeated along with the self-finger prick. Other tests may be repeated at clinician discretion. Participants unable to come to the clinic for the baseline visit, will be sent a home test kit for self-collected specimens. The kit will contain instructions on specimen collection for urine, throat and rectal swabs, and finger prick for dried blood spot and microtainer. The participant will mail the specimens back, using pre-paid mailer, to the lab for testing.

All participants will receive a follow-up call to receive lab results. Participants with low creatinine clearance (<60 ml/min) or who are positive for HIV will be ineligible, and referred to local clinical care, independent of study participation. Participants testing positive for STI, Hepatitis B, or Hepatitis C will be referred to local clinics that can provide treatment options for those with and without insurance, with clinic referrals provided by study staff experienced in providing linkage to care services. Participants who test positive for Hepatitis B will be counselled on the need to contact study staff if they plan on stopping PrEP.

Eligible participants will have a three-month prescription for PrEP sent to the pharmacy of their choice. The study will recommend pharmacies that can send prescriptions through the mail for participants interested in receiving their prescriptions in this manner. Participants will be reminded to submit a photo of their prescription label once they have received their prescription.

To optimize external generalizability, all participants will be provided standard of care PrEP navigation services. Navigation services will be delivered by study staff experienced in PrEP navigation with the goal of assisting patients in financial access to PrEP. The navigation will use

Gilead medication assistance and co-pay access programs, in addition to state-specific programs, to facilitate access to PrEP at low or no cost to participants. All study participants will be provided with identical PrEP navigation services that will assist with covering the costs of PrEP medication.

Participants will be randomized after all Baseline Visit procedures are complete and the participant has initiated PrEP. PrEP will not be provided to the participants as part of the study. The study purpose is to evaluate maintenance in PrEP care, using standard of care PrEP guidelines.

### **6.3 Follow-up Visits**

Follow-up visits (visits are defined as any interaction with the study data system) will be conducted at Months 1, 3, 6, 9, and 12 for those enrolled prior to May 2022 and 1, 3 and 6 Months for those enrolled after May 2022. The month 1 visit will consist of a brief survey for control participants, and a brief survey and clinical check-in for intervention participants. For intervention participants, home specimen kits for HIV and STI testing will be sent at months 3 and 6 for those enrolled after May 2022 as well as Months 9 and 12 for those enrolled prior to May 2022. Creatinine will be tested at month 3 for all participants as well as Month 9 for those enrolled prior to May 2022. Participants enrolled prior to May 2022 will complete surveys at months 3, 6, 9, and 12, and will use home specimen kit for DBS collection, TFV-DP testing, at months 6 and 12. Participants enrolled after May 2022 will complete surveys at months 3 and 6, and will use home specimen kit for DBS collection, TFV-DP testing at Month 6.

#### Home Care Kits:

For the intervention, the home care kits will consist of a self-collection of the following specimens: urine sample, rectal swab, pharyngeal swab, microtube blood collection, and dried blood spot collection. Instructions for self-collection of specimens will be available on the app and included in the kit. There will also be available to participants a call-in line to receive help with any unexpected problems in completing the kit during normal business hours. The kits will be tailored to the tests needed for each specific visit.

In collecting home specimens, participants will conduct 1-3 self-administered finger pricks, each one similar to the practice someone with diabetes might follow on a regular basis. The finger prick device will be spring-loaded and encased in a plastic shell, so participants will not see or manipulate the needle. Following the finger pricks, participants will collect 4-6 drops of blood by blotting their finger on collection paper, and by using a gravity-fed microtube. Participants will mail their biological specimens using pre-paid mailers included in the home kit. If an insufficient sample is collected at home, participants will be given an option to resend their sample or to take their lab tests at their provider's office.

Biological tests routinely performed at PrEP follow-up visits will be conducted on the mailed specimens from the home kit. Gonorrhea and Chlamydia tests will be performed on the urine sample and on the rectal and pharyngeal swabs. Syphilis testing and creatinine level will be performed using whole blood samples. HIV AbAg (4th gen) testing will be conducted from DBS cards. These tests will be conducted at a CLIA-certified laboratory.

Communication will be sent to participants through the app to confirm kit receipt and to remind participants to return their kit in a timely fashion.

Communication of results with providers will be accomplished through the secure clinician portal dashboard. Participants will be counselled as needed during follow-up visits regarding results and PrEP adherence.

#### Authorization for Release of Information:

All participants, in both intervention and control arms, will be contacted during the study period to fill out an optional Authorization for Release of Information form. This form will provide study staff with permission to contact each participant's pharmacy where they fill their current PrEP prescription. Participants will be asked to sign the form and provide contact information for their pharmacy (i.e. pharmacy name and number, address, and/or phone number). Study staff and clinicians will contact pharmacies to collect information on prescription fill dates and quantities. This information will be used to better understand study outcomes, particularly the primary adherence outcome for participants who have not returned their DBS cards.

#### **6.4 Referrals**

*During Study:* Treatment referrals will be provided to participants for positive STI laboratory results. Staff will work with local resources to facilitate access to care at free or low cost. In the case of a positive HIV test, participants will cease PrEP dosing, be discontinued from the study, and be linked to care the next business day. For positive STI tests, participants will have PrEP prescriptions initiated or renewed, and be referred to STI treatment at a local agency. Site study staff will follow-up with participants testing positive for STI to ensure they have sought appropriate care. In cases of participant-opted discontinuation of PrEP, the participant's rationale for discontinuing PrEP will be documented.

*End of Study:* Participants in the intervention arm will be linked to PrEP care by study staff. Control arm participants will continue with their regular care.

#### **6.5 Measures**

##### **6.5.1 Surveys**

As part of the PrEP@Home kit, participants will also complete an electronic survey through the app hosted on Alchemer.com. These surveys will include domains that physicians usually assess at quarterly PrEP follow-up visits, including sexual risk, illicit substance use risk, self-reported PrEP adherence, and any PrEP-related side effects. This information will be marked clearly in the survey as being shared with providers. Another section of the survey will involve research assessment and will not be transmitted to providers. This will include factors relevant to PrEP experience such as length of time on PrEP, as well as assessing participant experiences with and perceptions of the home kit. An additional cross-sectional survey will be emailed to participants to complete via Alchemer as a general assessment, PrEP, and behavior changes due to COVID19 public health restrictions.

##### **6.5.2 Outcome Measures**

Measurement of TFV-DP levels will be conducted for participants in both arms using liquid chromatography/tandem mass spectrometry methods on DBS samples. The primary outcome is protective levels of PrEP, as indicated by TFV-DP levels. TFV-DP level can be translated to an interpretation that indicates mean number of days per week PrEP is ingested over a time period of approximately 1-month preceding specimen collection. The cutpoint used for the primary outcome measure will be TFV-DP levels considered to be a surrogate for substantial protection:  
>700 fmol/punch, a level indicating >4 doses/wk.

#### **6.6 Training**

Recruiters and personnel staffing study data collection will complete CITI ethical conduct of research training, and also training on recruitment procedures and use of study instruments. Documentation of study staff training will be kept at each study site.

## **7. LABORATORY SPECIMENS AND PROCEDURES**

Baseline labs will be tested at each sites local laboratory. All study lab tests will be conducted at CLIA-certified laboratories using FDA-approved tests. Testing methods are specified for each site in Appendix 5.

### **7.1 HIV Testing**

HIV testing will be done for each study visit. All HIV testing will be conducted using a 4th generation Antibody Antigen (AbAg) test. An additional rapid HIV test may be used at the in-person baseline visit prior to determining eligibility to continue with the study. The HIV testing at follow-up visits for the intervention participants will be done using a self-finger prick collection and DBS card. Specimens with a reactive result will undergo confirmatory testing per CDC algorithm (Appendix 4) and participant will be asked to stop taking PrEP. If confirmed, results will be returned to participants by study staff experienced in HIV care linkage.

### **7.2 STI Testing**

All participants will be tested for Hepatitis B (HBsAg), Hepatitis C (anti-HCV), syphilis (EIA and RPR), and pharyngeal, urethral, and rectal gonorrhea and chlamydia at Baseline. Intervention participants will be tested for syphilis, gonorrhea, and chlamydia (pharyngeal, urethral and rectal) at quarterly follow-up visits.

### **7.3 Safety Labs**

Creatinine will be checked at baseline as part of eligibility and repeated at months 3 and 9 for safety. Creatinine will be tested using CLIA-certified FDA-approved tests. The creatinine clearance will be calculated using the Cockcroft and Gault equation and the participant's weight at baseline.

If creatinine clearance <60 ml/min on follow-up testing, the participant may need repeat testing and/or PrEP hold as per the prescribing physician's assessment and recommendation. Participant will be referred for further testing and management if needed.

### **7.4 Dried Blood Spots**

DBS cards will be collected from participants at months 6 and 12 for TFV-DP testing. The CLIA-certified UNC [name] Lab will perform testing on the DBS to assess TFV-DP levels, which will allow us to gain an understanding of participant adherence to their PrEP regimen. Participants will be informed of expectations regarding specimen collection at baseline. If we find higher rates of non-return of specimen cards for those who report cessation of PrEP care, we will consider increasing incentive payments to allow for collection of outcome data.

### **7.5 Biohazard Containment**

General (Baseline): each site has staff trained in biohazard handling who will be responsible for collecting specimens and preparing them for transport to the local laboratory for testing.

Home care: After collecting specimen(s) for testing, participants place the specimen collected in the provided packaging, which meets all federal regulations for shipment of Biological Substances, Category B (UN3373). Participants will ship their collected specimens in pre-paid mailers. Staff trained in biohazard handling will store specimens or ship them to the appropriate laboratory.

### **7.6 Future Storage**

Participants will be asked during the consenting process if they give permission to have samples stored for future research. DBS specimens collected from participants who agree to have samples stored for future use will be stored at Emory University or contracted laboratory. Personal identifying information will not be kept with the samples. These samples could assist with other research, such as DBS validation measures. Participants who do not agree to have specimens stored will have specimens discarded after lab tests are conducted.

## **8. SAFETY MONITORING AND ADVERSE EVENT REPORTING**

### **8.1 Data Safety Monitoring Board (DSMB)**

A DSMB will conduct interim monitoring of accumulating study data. The DSMB will receive standard data reports on a quarterly basis, with all serious adverse events reported in real time. The chair of the DSMB will lead biannual calls to discuss study progress, and the chair will convene additional DSMB meetings as needed based on interim reporting. Although the intervention is using an FDA-approved product for an approved indication, and care will be provided in line with guidance from the US Public Health Service using a CLIA-certified laboratory, a DSMB will be to provide several areas of oversight. The DSMB will be tasked with stopping the study if the intervention proves to be significantly outperforming the standard of care, or if the inverse occurs. The DSMB will monitor a number of factors, including HIV seroconversion, behavioral disinhibition, medication adherence, persistence in PrEP care, and differential loss to follow-up. The DSMB, comprised of experts on HIV prevention and PrEP, will incorporate the most current scientific advances in the rapidly changing field of PrEP in their study oversight. Prior to study launch, the DSMB will review all study protocols and manuals of operation.

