### 5.2 Randomization

Upon completion of stage 3 eligibility assessment (successful initiation of PrEP as determined by photo of prescription label), participants will be randomized to either intervention (PrEP@Home, n=264) or control (standard of care, n=132). Participants will be randomized using an electronic data system, DFExplore. We will implement a stratified randomization scheme using categories of age (18-34, 35-49) and study site to decreases the likelihood of Type I error due to the expected association between covariates and study outcome. An uneven allocation ratio of 2:1 (Intervention : Control) will facilitate subgroup analyses and modeling for Aims 2 and 3 by allowing for larger intervention group size.

All randomization will be accomplished within the study data management platform; within each stratum, the data system will produce a sequential block randomization list. This list, not viewable by study PI's or the study statistician, will automatically populate the appropriate study arm assignment in the electronic data system at the time each new participant is randomized at any of the four study sites.

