### 9.2 Power to detect effects in primary outcomes

A total of 396 participants will be enrolled at baseline to account for a 10% expected loss to followup during 12-months of study follow-up. With this sample size and assuming  $\alpha=0.05$  and two-sided significance, there will be 80% power to detect absolute differences between the intervention and control arms in the proportion of subjects with protective levels of TFV-DP of > 15.8% when the average proportion in the control group is 0.50. Power calculations were performed using PASS v.13 software (NCSS, LLC. Kaysville, Utah). Hypothesis is participants randomized to PrEP@Home will have higher levels of protection against HIV infection as

determined by levels of emtricitabine triphosphate (TFV-DP) than standard of care controls.

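### Section 8.1 has the DSMB stop for significance in either direction but sets no endpoint, number of looks or boundary, so the two-sided 0.05 in section 9 is not protected

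*Combined protocol and SAP*

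**What the plan says.** Section 8.1 gives the DSMB a comparative stopping task that runs both ways: "stopping the study if the intervention proves to be significantly outperforming the standard of care, or if the inverse occurs". On timing, "The DSMB will receive standard data reports on a quarterly basis"; the chair leads calls twice a year and may convene further meetings as needed. The factors to be watched include seroconversion, disinhibition, adherence, persistence and unequal loss to follow-up. The section does not say which of these drives the stopping decision, what test applies, or what counts as significant.

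Section 9.1 compares protective TFV-DP proportions with a pooled-variance z-test. It then fits a GLMM whose arm-by-time interaction is tested at 0.05, followed by either time-specific or main-effect tests. It mentions no interim analysis. Section 9.2 sets alpha at 0.05 and states: "two-sided significance, there will be 80% power to detect absolute differences between the intervention and control arms". The target is a gap of 15.8 points from a control proportion of 0.50. It makes no allowance for interim looks. No DSMB charter is cited.

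**The concern.** A rule to stop on significance, applied to accumulating data more than once, gives chance several opportunities to produce a difference. If the final test also stays at 0.05, the overall error must exceed 0.05. Because the rule works in both directions, the excess covers a false claim that PrEP@Home is better and a false claim that it is worse.

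There is a second consequence. Trials that stop early on a significance threshold overstate the effect on average. Section 9.4 takes the model's persistence and adherence parameters from the efficacy results and passes the model outputs to the cost-effectiveness analysis, so the overstatement would carry into Aims 2.3 and 3.

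**Working it through.** **1. The plan's own power figure.** Section 9.2 states: "A total of 396 participants will be enrolled at baseline to account for a 10% expected loss". Section 5.2 gives 264 intervention and 132 control. After 10% loss, 237.6 and 118.8 are analysed. The proportions are 0.658 and 0.50.

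- Pooled proportion: (118.8 × 0.50 + 237.6 × 0.658) / 356.4 = 0.6053
- Null SE: √[0.6053 × 0.3947 × (1/118.8 + 1/237.6)] = 0.05492
- Alternative SE: √[0.50 × 0.50/118.8 + 0.658 × 0.342/237.6] = 0.05524
- Power: Φ[(0.158 − 1.96 × 0.05492) / 0.05524] = Φ(0.91) = 81.9%

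The stated 80% is therefore reproduced to within 2 points, for one analysis at two-sided 0.05. The smallest difference detectable at 80% power is 15.4 points, against 15.8 stated.

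**2. How many looks the month-6 data support.** Section 3.3 gives 18 months of recruitment. Assume uniform accrual and no loss. The fraction of month-6 information at study month *m* is then (*m* − 6)/18. Biannual reviews at months 12, 18 and 24 give 1/3, 2/3 and 1: two interim looks and the final. Quarterly reviews from month 9 to month 24 give six.

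**3. Overall type I error.** Let B(t) be a Brownian motion with Z = B(t)/√t and limit c_k at look k. The density of paths not yet stopped is carried forward by

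f_k(b) = ∫ f_{k−1}(u) · φ[(b − u)/√(t_k − t_{k−1})] / √(t_k − t_{k−1}) du, over |u| < c_{k−1}√t_{k−1}.

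The overall error is 1 minus the integral of f_K over |b| < c_K√t_K. Looks are equally spaced and the count includes the final.

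| Looks | 1.96 at every look | 3.00 at interims, 1.96 at end |
|---|---|---|
| 1 | 5.0% | – |
| 2 | 8.3% | – |
| 3 (biannual) | 10.7% | 5.2% |
| 6 (quarterly) | 15.5% | 5.4% |

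**4. Overstatement after an early stop.** Take a true difference of 15.8 points, 80% fixed-design power (drift 1.960 + 0.842 = 2.802) and three looks at 1.96. About 66% of simulated trials stop before the end. Their mean estimate is 1.41 times the truth: 1.41 × 15.8 ≈ 22 points.

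**5. Cost of a proper boundary.** Three looks, starting from 80% power:

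| Rule | \|Z\| limits | Overall error | Power |
|---|---|---|---|
| O'Brien-Fleming | 3.471, 2.454, 2.004 | 5.0% | 79.3% |
| p<0.001 at interims | 3.29, 3.29, 1.96 | 5.05% | 80.0% |
| Pocock | 2.289 at each look | 5.0% | 73.4% |

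The single-analysis power in step 1 exceeds the stated 80% by 1.9 points, more than the 0.7 points O'Brien-Fleming costs.

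**The case against.** The strongest reply is that section 8.1 gives no interim p-value. Repeated testing at 0.05 is an inference, and a DSMB that quietly demanded |Z| ≥ 3 would leave the error at 5.2–5.4%. This stands as a limit on the size. It does not rescue the rule: the text requires no strict threshold, and 0.05 is the only level it offers.

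A reader might infer four biannual or eight quarterly looks, with errors of 12.6% or 17.6%. The documents do not support that for the month-6 outcome. Under the accrual assumed here those data are complete at about month 24, so later looks add no month-6 information and equal spacing fails. A reader might also treat each quarterly report as a test. Section 8.1 calls them standard data reports, section 8.2 ties quarterly reporting to adverse events, and study progress is discussed on the biannual calls. The biannual figure is the safer reading.

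It is also fair to say that a boundary may sit in a charter or manual outside these documents. None is cited, so the point is limited to the supplied text.

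Finally, forcing every harm comparison onto the month-6 proportion at biannual meetings would cut across the safety monitoring and as-needed meetings that section 8.1 provides. That objection is right, and the remedy below avoids it.

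**Conclusion.** The point holds. Section 8.1 states an actual comparative stopping rule with recurring review, and section 9 spends the full 0.05 at the end. Any interim chance of stopping for a difference then takes the overall error above 0.05, so this is a defect in the rule and not merely missing detail.

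The omission is certain; its size is conditional. At 0.05 per look the error is 8.3% with two looks and 10.7% with three biannual looks. It is 15.5% only if six quarterly reports are each tested, and 5.2–5.4% under a strict informal rule. These figures rest on uniform 18-month accrual, month-6 data and equally spaced looks, none of which the plan fixes for monitoring. The effect of watching several factors was not computed, because the stopping endpoint is not named. The documents do not support a flat statement that the trial will test repeatedly at 0.05.

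**What to change.** In sections 8.1 and 9.1, and in any DSMB charter:

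- State that stopping for comparative efficacy, in either direction, rests on the month-6 protective-level proportion at the planned biannual reviews. Month 6 is the one TFV-DP time point that participants enrolled before and after May 2022 share.
- Fix the number and timing of those reviews.
- Adopt either an O'Brien-Fleming-type spending function (at three looks, final |Z| about 2.00) or p<0.001 (|Z|>3.29) at interim looks with the final test at 0.05. The second option gives an overall error of about 5.05% at three looks.
- Say how the interim comparison links to the final test in 9.1, where a z-test, an interaction test and a branch to further tests now stand together.
- Keep between-arm efficacy significance tests out of the quarterly reports.
- Leave the DSMB's monitoring of seroconversion, disinhibition and differential loss, and its as-needed meetings, unrestricted.
- If between-arm comparisons have already been made, record how many and on which outcome.

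The cost is about one paragraph in each place. Early stopping for efficacy will need stronger evidence, and power falls by less than about 1 point. A strict boundary makes early stops rarer; it does not remove the overstatement in trials that do stop early.
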